11 STATISTICAL CONSIDERATIONS

11.1 Study Hypotheses

Primary objective (safety):

Null hypothesis: Rate of unacceptable safety events is $P > 30\%$
Alternative hypothesis: $P < 5\%$

Secondary objective (efficacy):

Null hypothesis: Response rate is $P \leq 40\%$
Alternative hypothesis: $P \geq 70\%$

11.2 Sample Size Considerations

We estimate, based on published results and our own experience, that 65% of all neonates born with vein of Galen malformation require urgent neonatal intervention (i.e. are NAR), under current standard of care. Thus, in order to achieve a cohort size of 20 treated patients, we expect to consent and screen 28-30 fetal patients. We expect to enroll 25 participants to account for withdrawals prior to completing the intervention (due to failure to achieve near ideal fetal position or other reasons). The study will be closed to enrollment once 20 participants have completed the intervention. Using the prescreening technique we have developed based on fetal MRI measurement of straight sinus or falcine sinus caliber at the narrowest point, we can estimate that 80% of all such fetal VOGM patients will progress to NAR status without fetal intervention. Setting a goal of reducing this fraction to 30% NAR status after fetal intervention (i.e., a 50% absolute reduction), the proposed sample size will provide 80% power to detect a significant effect of fetal intervention.

11.3 Safety Review

Two-stage design for safety endpoint

In Stage 1, up to 11 evaluable patients will be enrolled (**Table 2**). Out of 11 patients, if 3 or more patients experience an unacceptable event (see definition in Section 3.2 above and recapitulated below Table 2), the intervention is unsafe and not worthy of further study. If 2 or fewer experience any unacceptable event, the trial will proceed to Stage 2, where an additional 9 evaluable patients will be enrolled, for a total of $N=20$ evaluable patients. Out of $N=20$ patients, if 4 or more patients experience any unacceptable event, the intervention is unsafe and not worthy of further study. If 3 or fewer patients experience any unacceptable event, the intervention is sufficiently safe and worthy of further study. In addition, in case of a single maternal death, the study will be halted pending review by the DSMB and the FDA.

This design tests the null hypothesis that the rate of unacceptable events is $P > 30\%$ versus the alternative that $P < 5\%$. The total type I error rate is 0.097 and the power is 97.5%. If the intervention is truly unsafe, there is a 68.7% probability of early trial termination.

Table 2: Decision rules for safety based on the optimum two-stage design.

	Cumulative number of patients with unacceptable events	Decision
Stage 1: Enroll 11 patients	3 or more	Terminate the trial: agent not worthy of further study
	2 or fewer	Inconclusive result: proceed to Stage 2
Stage 2: Enroll 9 additional patients	4 or more	Terminate the trial: agent not worthy of further study
	3 or fewer	Trial concludes: agent worthy of further study

- 1) Unacceptable events within 7 days of fetal embolization include:
 - a) Fetal death
 - b) Fetal intracranial hemorrhage, either parenchymal or extra-axial, other than petechial hemorrhage. A petechial hemorrhage is seen as focal staining of the brain parenchyma by blood products on MRI, is not associated with mass effect, and there are minimal neurologic sequelae. Petechial hemorrhages are usually considered non-serious adverse events in trials.
 - c) Maternal death
- 2) Unacceptable events occur between fetal embolization and delivery include:
 - a) Intra-procedural and post-procedural morbidity to the fetus and mother, probably related to the fetal intervention, e.g. placental abruption with subsequent sequelae
 - b) Preterm delivery < 28 weeks, probably related to the fetal intervention
 - c) Maternal blood transfusion or unanticipated surgical intervention, probably related to the fetal intervention
 - d) Presence of fetal imaging evidence of new brain injury in a location or pattern unexpected for the natural history of vein of Galen malformation, probably related to the fetal intervention

11.4 Efficacy Review

Two-stage design for efficacy endpoint

In Stage 1, up to 11 evaluable patients will be enrolled (**Table 3**). Out of 11 patients, if 5 or fewer patients respond, i.e. do not experience a serious postnatal event (see definition in Section 3.2 above), the intervention is not efficacious and not worthy of further study. If 6 or more respond, the trial will proceed to Stage 2, where an additional 9 evaluable patients will be enrolled, for a total of N=20 evaluable patients. Out of N=20 patients, if 10 or fewer patients respond, the intervention is not sufficiently efficacious and not worthy of further study. If 11 or more patients respond, the intervention is sufficiently efficacious and worthy of further study.

This design tests the null hypothesis that the response rate is $P \leq 40\%$ versus the alternative that $P \geq 70\%$. The total type I error rate is 0.099 and the power is 90.2%. If the intervention is truly not efficacious, there is a 75.3% probability of early trial termination.

Table 3: Decision rules for efficacy based on the optimum two-stage design.

	Cumulative number of responses	Cumulative number of non-responders (patients with serious postnatal events)	Decision
Stage 1: Enroll 11 patients	5 or fewer	6 or more	Terminate the trial: fetal intervention not worthy of further study
	6 or more	5 or fewer	Inconclusive result: proceed to Stage 2
Stage 2: Enroll 9 additional patients	10 or fewer	10 or more	Terminate the trial: fetal intervention not worthy of further study
	11 or more	9 or fewer	Trial concludes: fetal intervention worthy of further study

11.5 Timing of safety and efficacy rules

The safety endpoint is observed from Day 0 (the day of fetal intervention) to Day 7 post-intervention. The efficacy endpoint is observed from the birth to Day 30 of life. Both safety and efficacy decision rules must be satisfied before enrollment to Stage 2 is allowed. Prior to initiating accrual at Stage 2, a sensitivity analysis will be performed to determine if both the safety and efficacy rules would be triggered. Hence, trial enrollment for Stage 2 may be suspended after the enrollment of the 11th patient to allow observation up to Day 30 of life of the most recently treated patient.

The safety and efficacy rules are to be interpreted as specifying that the trial will stop as soon as either criterion is reached; e.g., if the first 3 evaluable patients experience unacceptable prenatal events (safety rule), or the first 6 patients experience serious postnatal events (efficacy rule), then the trial stops immediately. Beyond the 11th patient, the trial halts as soon as 4 unacceptable prenatal events or 10 serious postnatal events occur.

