3.2 Study Outcome Measures

Primary (safety) endpoint: The procedure is deemed safe if

- 1) **None** of the following unacceptable events occur within 7 days of fetal embolization:
 - a) Fetal death
 - b) Fetal intracranial hemorrhage, either parenchymal or extra-axial, other than petechial hemorrhage. A petechial hemorrhage is seen as focal staining of the brain parenchyma by blood products on MRI, is not associated with mass effect, and there are minimal neurologic sequelae. Petechial hemorrhages are usually considered non-serious adverse events in trials.
 - c) Maternal death
- 2) **None** of the following unacceptable events occur between fetal embolization and delivery:
 - a) Intra-procedural and post-procedural morbidity to the fetus and mother, probably related to the fetal intervention, e.g. placental abruption with subsequent sequelae
 - b) Preterm delivery < 28 weeks, probably related to the fetal intervention
 - c) Maternal blood transfusion or unanticipated surgical intervention, probably related to the fetal intervention
 - d) Presence of fetal imaging evidence of new brain injury in a location or pattern unexpected for the natural history of vein of Galen malformation, probably related to the fetal intervention

Secondary (efficacy) endpoint: The procedure is deemed efficacious if **none** of the following serious postnatal events occur within 30 days of birth:

1. Urgent neonatal embolization is needed. Without fetal intervention, we'd expect 80% of the cohort to require such intervention.
2. Neonatal death. Without fetal intervention, we'd expect a mortality rate of 40% in this cohort.
3. Brain MRI within the first three weeks after birth reveals parenchymal brain injury (acute infarct or gliosis) affecting > 10% of the supratentorial brain volume. Without fetal intervention, we'd expect 30% of patients in this cohort to show this kind of injury.

Additional efficacy data to be collected includes assessment of the neurocognitive development in the treated cohort. Subjects will be followed and assessed until age 24 months and results will be compared to historical controls of NAR VOGM patients treated using the current neonatal paradigm.

Comparison of outcomes will be made with published (meta-analysis and UK national data [1, 2, 6, 7]) and institutional historical results for fetuses who receive standard neonatal or post-neonatal treatment.

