7.2 Study Intervention (Visit 2)

Study Procedure Visit

- Perform a preprocedure assessment on the mother
- Obtain clinical procedural consent and anesthesia consent
- Perform the study intervention

After the intervention

- Mothers will be monitored at least overnight at BWH or BCH, or longer if needed
- Tocolytic medication will be administered perioperatively and as needed for the first 12 hours post-intervention
- Fetal heart rate will be monitored continuously after the procedure
- Focused ultrasound to look at cervix, placenta and fetal brain will be performed 3-6 hours post-procedure
- Fetal ultrasound, fetal echocardiogram, and fetal MRI will be performed 24-28 hours after the procedure
- Fetal distress will be addressed clinically and as appropriate for gestational age and status of vein of Galen malformation
- Preterm labor, rupture of membranes and abruption will be addressed clinically, as appropriate for gestational age

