7.3 Pre-Delivery Follow up visits

If more than 4 weeks remain before expected delivery, the following assessments will be repeated every 4 weeks until delivery:

- Fetal ultrasound, fetal echocardiogram, and fetal MRI

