7.4 Delivery

Plans will be made for all subjects to be delivered at BWH. The mode of delivery is not impacted by the fetal intervention and will be determined based on clinical criteria. Likewise, gestational age of delivery will be determined clinically. Depending on the specifics of each case, including how far along the pregnancy is, how severely affected the fetus is, and other factors, in some cases, early delivery would be the chosen option, while in others, termination might be the recommended option, as previously discussed by the subject with the clinical care team. A recommendation of termination of pregnancy would result from major cerebral injury (intracranial hemorrhage other than petechial or parenchymal infarct >10% of the supratentorial brain volume) visualized on fetal imaging, in the setting of a gestational age young enough that termination remains an option. As such major cerebral injury is one of the unacceptable safety events mentioned above in Section 3.2 and below in Section 11.3, the subject in question would be included in the calculations related to the two-stage study design for safety. However, since fetal death would not have been spontaneous but rather by termination of pregnancy, the subject would not be counted towards the fetal deaths in the study.

If no such situation arises, elective delivery will be performed on a date chosen by the obstetrician as optimal in terms of safety for the mother and baby, in the same way that delivery dates are chosen for patients with vein of Galen malformations who do not undergo fetal intervention.

The newborn will be admitted to the NICU, as per the current practice for all patients with VOGM. As per clinical care, an MRI and echocardiogram will be performed as soon as possible after delivery, typically on day 1 of postnatal life. All care, including additional embolization procedures and additional imaging, will be done per standard of care for this patient population. Per our protocol (and similar to that of most major referral centers for VOGM), if a neonatal patient is unable to be extubated or is not stable enough on medications to be discharged from the NICU within a week due to cardiopulmonary failure, this indicates a need for urgent neonatal embolization.

At our center, extubation criteria in neonates without an underlying lung disease include:

- Patient awake with spontaneous and regular breaths, and
- Mean airway pressure on the ventilator < 10 cmH₂O and FiO₂ < 0.25

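### Section 11.5 ends the safety endpoint at Day 7, while Sections 3.2 and 11.3 follow four of its seven components to delivery

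*Combined protocol and SAP*

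**What the plan says.** Section 11.5, which sets the timing of the decision rules, gives one window for the whole safety endpoint: "The safety endpoint is observed from Day 0 (the day of fetal intervention) to Day 7 post-intervention".

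Section 3.2 defines the endpoint in two parts:

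- **Part 1, 7 days (three components):** fetal death, non-petechial fetal intracranial hemorrhage, maternal death.
- **Part 2, to delivery (four components, each judged probably related to the intervention):** maternal or fetal morbidity, delivery before 28 weeks, maternal transfusion or unplanned surgery, and unexpected new brain injury on fetal imaging. The requirement is that none "of the following unacceptable events occur between fetal embolization and delivery".

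Section 11.3 repeats both lists under Table 2 and introduces the second with "Unacceptable events occur between fetal embolization and delivery include". Section 7.4, on which subjects enter the two-stage safety calculation, calls major cerebral injury "one of the unacceptable safety events mentioned above in Section 3.2 and below in Section 11.3".

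The counting unit also varies. Tables 2 and 3 count patients. The last sentence of 11.5, which applies after the 11th patient, says "the trial halts as soon as 4 unacceptable prenatal events or 10 serious postnatal events occur".

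**The concern.** The safety endpoint is primary and drives the 3-of-11 and 4-of-20 limits. Under 11.5 as written, a related event first arising after Day 7 counts toward neither limit. Under 3.2 and 11.3 it counts toward both. The error can only run toward missing harm, in a trial of a procedure with no earlier fetal use.

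The gap is most concrete for new brain injury. After the procedure, Section 7.2 schedules the following: "Fetal ultrasound, fetal echocardiogram, and fetal MRI will be performed 24-28 hours after the procedure". That is the only scheduled fetal MRI within Day 0 to 7. Section 7.3 adds: "If more than 4 weeks remain before expected delivery, the following assessments will be repeated every 4 weeks until delivery". An injury first seen on one of those later scans counts under 3.2 and 11.3 but not under 11.5. The preterm component is exposed only for fetuses treated before 27 weeks, because 28 weeks must fall more than 7 days after treatment; entry opens at 23 weeks.

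On the counting unit, one neonate can have more than one listed postnatal event, such as urgent embolization and death. Events and patients can therefore differ.

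**Working it through.** **Inputs (Section 11.3).** Unacceptable rate p0 = 30%, acceptable rate p1 = 5%. Stop if 3 or more of 11 patients have an event; declare unsafe if 4 or more of 20 do.

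**Formulas.** Let X1 ~ Bin(11, p) and X2 ~ Bin(9, p), counting each patient once.

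- P(declared safe) = Σ over x = 0, 1, 2 of P(X1 = x) × P(X2 ≤ 3 − x)
- P(stop at Stage 1) = 1 − P(X1 ≤ 2)

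**The plan's own figures.**

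- p = 0.30: 0.01977 × 0.72966 + 0.09322 × 0.46283 + 0.19975 × 0.19600 = 0.0967 (stated 0.097). Stage 1 stop: 1 − (0.01977 + 0.09322 + 0.19975) = 0.6873 (stated 68.7%).
- p = 0.05: 0.56880 × 0.99936 + 0.32931 × 0.99164 + 0.08666 × 0.92879 = 0.9755 (stated 97.5%).

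All three reproduce with patients as the unit, so the design figures are sound.

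**Applying the Day 7 window.** Keep the true through-delivery rate at 30%. Assume that L percentage points come from patients whose only qualifying event falls after Day 7. The documents give no value for L. The counted rate becomes 30% − L under the same rule:

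| L (points) | Counted rate | P(declared safe) | P(stop at Stage 1) |
|---|---|---|---|
| 0 | 30% | 9.7% | 68.7% |
| 1 | 29% | 11.4% | 66.1% |
| 3 | 27% | 15.5% | 60.5% |
| 5 | 25% | 20.6% | 54.5% |
| 10 | 20% | 38.2% | 38.3% |
| 15 | 15% | 61.3% | 22.1% |

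**Mixed reading.** Suppose only the Stage 1 look uses Day 7 and the final 4-of-20 count runs to delivery. For the same L (1 to 15), P(declared safe) is 9.8%, 10.0%, 10.1%, 10.4% and 10.6%. The false-safe rate barely moves. What is lost is the Stage 1 stop, as in the last column above.

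**Counting events after patient 11.** Keep Stage 1 in patients. For the final limits (4 prenatal, 10 postnatal), assume a share q of affected patients have two events:

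| q (assumed) | Efficacy power at 70% response | Safety power at 5% |
|---|---|---|
| 0 | 90.2% | 97.5% |
| 10% | 85.2% | 96.0% |
| 25% | 75.4% | 93.4% |
| 50% | 57.4% | 88.4% |

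The row q = 0 reproduces the powers stated in 11.3 and 11.4, which confirms that the design was computed in patients.

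**The case against.** The strongest reply is that this is one loose sentence set against a definition given twice.

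- **Intent.** Section 11.5 itself later speaks of prenatal events, the primary objective is prenatal safety, and 11.3 prints the full definition directly under Table 2. A statistician applying that table would probably use it. This is good evidence of intent, but it also means that 11.5 is wrong as written.
- **The Stage 1 gate.** Section 11.5 requires both rules to be met before Stage 2, and efficacy runs to Day 30 of life, so delivery data on the first 11 patients should exist by then. This blunts the Stage 1 concern. But having the data does not widen an endpoint defined as closing at Day 7, and the hold is optional in wording: "trial enrollment for Stage 2 may be suspended after the enrollment of the 11th patient". The gate also does not settle which events enter the final 4-of-20 count.
- **Other protection.** Section 7.4 keeps in the safety count a subject whose pregnancy ends after major cerebral injury, with no Day 7 limit. The DSMB is notified of every serious adverse event and judges whether the stopping criteria are met. This limits practical harm but does not repair the formal count.
- **Magnitude.** The largest figures need a third to a half of affected patients to have their only event after Day 7, which nothing in the documents supports. The late components must also be probably related to the intervention, and repeat MRI is scheduled only when more than 4 weeks remain. This is fair: the upper rows show a range, not a forecast.
- **Events versus patients.** The preceding sentence of 11.5, both tables and the reproduced error rates all point to patients. That stands, so this is a wording correction only.

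**Conclusion.** The concern holds. Section 11.5 misstates the observation window for four of the seven components of the primary safety endpoint, and this must be fixed. That conclusion rests on the text alone. The stated error rates, limits and sample size are right for the endpoint in 3.2 and 11.3.

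The size depends on the unknown share of events first arising after Day 7. It is small if 1 to 3 of the 30 points are late and large if 10 or more are. The unit mismatch in the last sentence of 11.5 is secondary and adds nothing to the severity.

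**What to change.** Reconcile 11.5 with 3.2, 11.3 and Tables 2 and 3:

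1. State that each safety component is observed over its Section 3.2 window: 7 days for part 1, through delivery for part 2.
2. State that an event counts toward the limits as soon as it occurs, but that a patient is classed as event-free only at delivery.
3. Reword the last sentence to refer to 4 patients with an unacceptable prenatal event or 10 patients with a serious postnatal event.

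The cost is two or three sentences, with no change to thresholds, sample size or stated error rates. The Stage 1 and final safety decisions must wait for delivery. At Stage 1 this adds little, since the efficacy rule already needs data to Day 30 of life, but the delay is not certain to be zero because the enrollment hold is worded as optional.

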5.1 Subject Inclusion Criteria

In order to be eligible to participate in this study, an individual must meet all of the following criteria:

1. *Pregnant woman carrying a fetus harboring a vein of Galen malformation in whom the straight sinus or falcine sinus draining the prosencephalic varix measures 7 mm or more on fetal MRI (medio-lateral diameter measured at the narrowest point of the sinus along the rostral-caudal axis, assessed on a T2-weighted coronal slice).*
2. *Fetal gestational age between 23 weeks and term as determined by clinical information and evaluation of first ultrasound.* Although it is believed that the VOGM forms between gestational weeks 6-11 (the developmental window during which the prosencephalic vein of Markowski is present before involution [17]), diagnosis of the condition by fetal ultrasound has never been reported prior to 22 weeks, likely because of the small size of the varix prior to that point. In principle, embolization of the malformation at any time after identification and prior to delivery could forestall the development of brain, cardiopulmonary, and other organ injury. The presence of the low-pressure placental circulation and the fetal lower-flow baseline cerebral circulation might be protective, in terms of reducing potential morbidity from intracranial hemodynamic shifts that accompany embolization. The suitability for fetal treatment, in terms of technical/positional factors, will be assessed on a case-by-case basis by the MFM, ultrasonographer, and neurointerventionalist participating in the study.
3. *Anatomic diagnosis of fetal vein of Galen malformation.* Various cerebrovascular conditions, such as dural sinus malformation and pial arteriovenous fistula, can result in dilated intracranial vascular structures being visualized in utero. Similarly, fetal dilatation

of the vein of Galen can occasionally be seen without the presence of an arteriovenous lesion at all, as a benign venous variant. This condition is readily distinguishable sonographically from VOGM by virtue of the presence of dilated arterial feeding pedicles, and by the presence of an arterial waveform within the varix. This study is aimed solely at fetuses with an established diagnosis of vein of Galen malformation.

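### Section 11.5 ends an optional Stage 2 pause at Day 30 of the most recently treated patient, but Stage 1 outcomes mature in birth order; the mandatory gate protects efficacy and leaves a small gap, mainly on safety

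*Combined protocol and SAP*

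**What the plan says.** All references are to the combined protocol and SAP.

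- **The gate (11.5).** "Both safety and efficacy decision rules must be satisfied before enrollment to Stage 2 is allowed". A sensitivity analysis of both rules precedes Stage 2 accrual, but the section does not say how a patient with a pending outcome is counted.
- **The pause (11.5).** Stage 2 enrollment "may be suspended after the enrollment of the 11th patient to allow observation up to Day 30 of life of the most recently treated patient".
- **Efficacy clock (11.5).** "The efficacy endpoint is observed from the birth to Day 30 of life".
- **The Stage 1 efficacy rule (11.4).** "Out of 11 patients, if 5 or fewer patients respond", the intervention is declared not efficacious; 6 or more responses open Stage 2.
- **Treatment and delivery.** Inclusion criterion 2 (5.1) reads "Fetal gestational age between 23 weeks and term as determined by clinical information and evaluation of first ultrasound". Under 7.4, "gestational age of delivery will be determined clinically".
- **The safety window.** Section 11.5 states: "The safety endpoint is observed from Day 0 (the day of fetal intervention) to Day 7 post-intervention". The second part of the endpoint in 3.2, repeated in 11.3, requires that none "of the following unacceptable events occur between fetal embolization and delivery".
- **Limits after the 11th patient (11.5).** The trial halts at 4 unacceptable prenatal events or 10 serious postnatal events. The Stage 1 limits are 3 and 6.

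**The concern.** The pause waits for the patient treated last, whereas the efficacy result comes last from the patient born last. With treatment possible over more than three months of gestation, the two need not coincide. Nothing in the plan states that all 11 Stage 1 patients must have reached Day 30 before Stage 2 opens, and the pause itself is only permitted, not required.

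The operating characteristics in 11.3 and 11.4 assume that all 11 Stage 1 outcomes are available at the interim decision. If Stage 2 opens with an outcome pending, further mothers and fetuses could be treated in a trial that the complete Stage 1 data would have stopped. A late event from the first 11 patients would then be counted against the looser limits that apply after the 11th patient.

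**Working it through.** **1. The plan's own figures.** Exact two-stage binomial sums reproduce them.

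| Rule | Type I error | Power | Early stop at the null |
|---|---|---|---|
| Efficacy (5/11, 10/20; 40% vs 70%) | 0.099 | 90.2% | 75.3% |
| Safety (stop at 3/11 or 4/20; 30% vs 5%) | 0.097 | 97.5% | 68.7% |

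The design is correctly calculated. The question is whether the timing text delivers it.

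**2. Date arithmetic.** Assume delivery at 38 weeks. Patient 10 is treated at 24 weeks (week 0) and patient 11 four weeks later at 36 weeks.

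- Patient 11: born in week 4 + (38 − 36) = 6; Day 30 at 6 + 30/7 = week 10.3.
- Patient 10: born in week 38 − 24 = 14; Day 30 at 14 + 30/7 = week 18.3.

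The pause can end in week 10.3 with patient 10 still in utero. Efficacy and the to-delivery part of safety are then both open for that patient.

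**3. How often.** The documents give 20 treated patients over 5 to 7 years: 20/7 = 2.9 to 20/5 = 4 a year. The gestational ages are assumptions, because the documents give only ranges. Simulation: 200,000 trials, exponential gaps between treatments, uniform gestational age at treatment, delivery at 36 to 39 weeks.

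| Assumed treatment window | An earlier-treated patient is short of Day 30 when patient 11 reaches it |
|---|---|
| 23–37 weeks | 12–16% |
| 30–36 weeks | 6–8% |

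A wider set of assumptions (treatment windows from 30–36 to 23–39 weeks, fixed delivery at 37 to 39 weeks) gives 5 to 17%, with a patient still in utero in 0.1 to 7%. Usually only one patient is pending. A 12th patient is treated in that interval, from ordering alone, in about 0.5 to 4% of trials.

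If the optional pause is not used at all, at least one Stage 1 outcome is still open when the next patient would be treated in 38 to 68% of simulated trials. That range covers 2.9 to 5 treatments a year, so its upper end lies above the planned rate. The gate would still apply in those trials.

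**4. Efficacy with one outcome pending, at 40% response.** Among the 10 known outcomes:

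- 6 or more responses: 16.6%. The rule is met whatever the pending result.
- 5 responses and 5 failures: 20.1%. The rule is undetermined.
- 6 or more failures: 63.3%. The stopping limit is reached.

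Under the strict gate Stage 2 opens only in the first case, so the efficacy decision is unaffected. If having hit no limit yet were taken as satisfying the rule, and the Stage 1 rule were not applied again, Stage 2 would open in 16.6 + 20.1 = 36.7% instead of 24.7%. Early stopping would be 63.3% instead of 75.3%, and type I error 0.111 instead of 0.099. The difference in early stopping is the 5/5 split followed by a failure: 0.201 × 0.60 = 0.120.

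That figure is conditional on a pending patient. Over all null trials on this loose reading, the loss is about 0.06 × 0.120 = 0.7 to 0.16 × 0.120 = 1.9 percentage points.

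**5. Safety with one patient pending, at a 30% event rate.** Stage 2 can open with 2 events among the 10 known patients (probability 0.233), and the pending patient supplies the third: 0.233 × 0.30 = 0.070. Early stopping is then 61.7% instead of 68.7%, and type I error 0.0995 instead of 0.097. This is an upper bound, since part of the pending patient's risk falls in the first 7 days and is already observed. With a patient in utero in at most 7% of trials, the ordering effect reaches at most 0.07 × 0.070 = 0.5% of null trials.

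**The case against.** The strongest reply is that the pause sentence is subordinate to the gate. Both rules must be satisfied, and 11.4 defines satisfied as 6 or more responses. With 5 responses, 5 failures and one outcome pending, the efficacy rule is not met and Stage 2 stays closed. With 6 known responses, waiting changes nothing, so a permissive pause is coherent. A check of both rules is also required before Stage 2 accrual. Under section 9 the DSMB reviews stopping criteria after each serious adverse event, and its charter, not available here, may add more. The reference to the 11th patient can fairly be read as the 11th evaluable patient, since 11.3 and 11.4 define Stage 1 that way.

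This stands for efficacy. A reader might infer that the plan as written lowers early termination from 75.3% to 63.3%. The documents do not support that: the figure needs one outcome pending and also a reading on which an undetermined rule counts as satisfied.

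The reply does not settle safety. Section 11.5 treats the safety endpoint as complete at Day 7, so the safety rule can be declared satisfied for a patient who remains at risk until delivery under 3.2. A third Stage 1 event arriving after that point would meet a limit of 4. Nor does the section say how pending patients enter the sensitivity analysis.

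**Conclusion.** The defect is real but narrow. The pause is tied to the wrong patient, and an earlier-treated Stage 1 patient can be pending when it ends in about 6 to 16% of trials at the planned accrual. A 12th treatment before all outcomes are known, from ordering alone, occurs in about 0.5 to 4%. These frequencies rest on assumed gestational ages at treatment and delivery and on random accrual.

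Read strictly, the gate keeps the efficacy decision and its stated error rates intact. The remaining gap has three parts: an optional pause under a mandatory gate, a safety window that ends at Day 7 in 11.5 and at delivery in 3.2, and looser limits for late events from the first 11 patients. With the pause in use, the numerical effect on the error rates is small. The wording still matters because this is the only formal interim gate in a first-in-fetus trial. Severity: minor to moderate.

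**What to change.** Replace the pause sentence in 11.5 with text to this effect: Stage 2 enrollment will be suspended once 11 evaluable patients have been treated, until all 11 have completed the safety window to delivery and have reached Day 30 of life or had an endpoint event, unless the outcomes in hand already satisfy both Stage 1 rules whatever the pending results. Add that late outcomes from the first 11 patients are judged against the Stage 1 limits of 3 safety events and 6 efficacy failures. Bring the safety window in 11.5 into line with 3.2 and 11.3.

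Sample size, decision limits and stated error rates are unchanged; the trial would then run as those figures assume. The cost is a pause longer by a few weeks in a minority of trials (3.7 weeks on average where it applies, with treatment at 23–37 weeks), against 5 to 7 years of recruitment. The exception avoids waiting when pending results cannot matter.
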